## 17.0 Confidentiality

17.1 *Data Security:* All data will be stored on servers (Redcap and CTSI AHC-IE data shelter) managed by the University of Minnesota IS. No data will be stored on individual research computers, flash drives, etc. These servers Redcap and the data shelter meet all data regulatory requirements and are HIPAA compliant.

## 18.0 Provisions to Monitor the Data to Ensure the Safety of Participants

18.1 *Integrity Monitoring:* Data entry will be performed by trained members of the research team who have received documented delegation of authority. Data integrity will be overseen by the PIs and the Minnesota CCBR. A study monitor will review 100% of electronic consent documents, study drug administration data, and SAE reporting. Additionally, a random sampling of 5% of subjects will undergo full evaluation and comparison of source documentation with data entered into the study database. The first data monitoring visit will be scheduled once 10% of the cohort has been enrolled, with repeat monitoring after 50% and 100% of enrollments. Monitors will evaluate 100% of users to ensure assigned access is consistent with training and delegation of authority logs. The project research coordinators at the sites will maintain binders containing pertinent documents and information including IRB approval letters, documentation of GCP training, licenses, human subjects research ethics training certificates, curriculum vitae, and correspondence.

### 18.2 Adverse events reporting

- *Definition of an Adverse Event (AE):* An AE is any symptom, sign, illness, or experience that develops or worsens in severity during the course of the study but does not necessarily have a causal relationship with study agent/intervention or procedures. A clinical trial adverse event is defined as any untoward medical event associated with the use of a drug or study procedure. The Investigators will determine daily if any adverse events occur during the period from enrollment (signing of the informed consent) through study day 15. Investigators will determine if the event is serious or related to the study drug. The rationale for this time window is the half-life of 2 hours for losartan and 6-9 hours for its metabolite. Even in the setting of impaired clearance, 3 days after study drug cessation is more than adequate to help to define the period at risk from losartan. Abnormal results of diagnostic procedures are considered to be AEs if the abnormality:

- results in study withdrawal,

MEDICAL PROTOCOL (HRP-590)

SHORT PROTOCOL TITLE: Randomized control trial of losartan for inpatients with COVID-19

VERSION DATE:22APR2020

- is associated with a serious adverse event (SAE),
- leads to additional treatment or to further diagnostic tests, or
- is considered by the Investigator to be of clinical significance.

- **Definition of a Serious Adverse Event:** Adverse events are classified as serious or non-serious. An SAE is any AE that is:

- *Fatal,*
- *life-threatening,*
- *requires or prolongs a hospital stay,*
- *results in persistent or significant disability or incapacity,*
- *a congenital anomaly or birth defect, or*
- *an important medical event.*

Important medical events are those that may not be immediately life threatening, but are clearly of major clinical significance. They may jeopardize the subject, and may require intervention to prevent 1 of the other serious outcomes noted above. For example, drug overdose or abuse, a seizure that did not result in in-patient hospitalization, or intensive treatment of bronchospasm in an emergency department would typically be considered serious. Serious adverse events will be collected during the first 15 study days, regardless of the investigator's opinion of causation. Thereafter, serious adverse events are not required to be reported unless the investigator feels the events were related to either study drug or a protocol procedure.

Study site personnel must alert a study investigator of any serious and study drug or study procedure related adverse event within 24 hours of investigator awareness of the event. Alerts issued via telephone are to be immediately followed with official notification on the adverse event case report form.

All AEs that do not meet any of the criteria for serious should be regarded as non-serious AEs.

- **Preexisting Condition:** A preexisting condition is one that is present at the start of the study. A preexisting condition will be recorded as an AE if the frequency, intensity, or the character of the condition worsens during the study period.

- **Post-study Adverse Event:** All unresolved AEs will be followed by the Investigator until the events are resolved, the subject is lost to follow-up, or the AE is otherwise explained. At the last scheduled visit, study personnel will instruct each subject to report any subsequent event(s) within 3 months of study completion that the subject, or the subject's personal physician, believes might reasonably be related to participation in this study.

- ***Abnormal Laboratory Values:*** A clinical laboratory abnormality should be documented as an AE if any 1 of the following conditions is met:
  - The abnormality suggests a disease and/or organ toxicity that worsened from the time of enrollment, or
  - The abnormality is of a degree that requires active management; e.g., change of dose, discontinuation of the drug, more frequent follow-up assessments, further diagnostic investigation, etc.
- ***Continuous SAEs of interest monitoring:*** The following SAEs will be continuously reported to the DSMB: deaths. Cardiovascular events (need for vasoactive drugs or fluids for hypotension), and respiratory events (worsening hypoxia, worsening acute respiratory distress syndrome, or new respiratory failure) will be continuously reported to the DSMB within 24 hours of recognition for safety reasons. While they will be reported continuously, they will not necessarily be filed as SAEs unless the investigator deems it to be related to study procedures (see below)
- ***Other outcomes that may be exempt from adverse event reporting:*** Study specific outcomes as outlined in 5.1 and 5.2 are exempt from adverse event reporting unless the investigator deems the event to be related to the study procedures (or of uncertain relationship) or if the event leads to discontinuation of study procedures. The following are examples of events that will be considered study specific clinical outcomes and will be systematically tracked through the study design. The rationale for this criteria is that these events are likely to be present in a large proportion of the study population, and relatedness will be subject to significant subjective assessment, making adverse event reporting can be sporadic and inconsistent. Therefore, events more likely to be truly related to a study intervention are better treated by consistent tracking through the systemic design and collection of potentially related adverse events:
  - Respiratory events: decreased PaO2/FiO2, hypoxia, worsening acute respiratory distress syndrome, or respiratory failure.
  - Cardiovascular events: (need for vasoactive drugs or fluids for hypotension)
  - Hepatic events: hepatic injury or liver dysfunction that leads to an increase from baseline in the serum level of bilirubin.
  - Renal events: renal failure, renal insufficiency, or renal injury that leads to an increase from baseline in serum creatinine.
  - Hematologic/coagulation events: coagulopathy, disseminated intravascular coagulation, thrombocytopenia, or thrombocytosis.
  - Changes in serum sodium and potassium
- ***Scales Used to Grade Severity of Adverse Events:*** All AEs will be graded in the following manner:
  - Grade 1 (Mild): Events require minimal or no treatment and do not interfere with the participant's daily activities.
  - Grade 2 (Moderate): Events result in a low level of inconvenience or concern. Moderate events may cause some interference with functioning.

- Grade 3 (Severe): Events interrupt a participant's usual daily activity and may require systemic drug therapy or other treatment. Severe events are usually incapacitating.
- Grade 4 (Life-threatening): Any adverse drug experience that places the participant, in the view of the Investigator, at immediate risk of death from the reaction as it occurred (i.e., it does not include a reaction that had it occurred in a more severe form, might have caused death).
- Grade 5 (Death)
- **Scales Used Attribute Adverse Events:** The Principal Investigator will assess the relationship of all AEs to any drug or study procedure:
  - Definitely Related: There is clear evidence to suggest a causal relationship, and other possible contributing factors can be ruled out. The clinical event, including an abnormal laboratory test result, occurs in a plausible time relationship to study agent/intervention administration and cannot be explained by concurrent disease or other drugs or chemicals. The response to withdrawal of the study agent/intervention (de-challenge) should be clinically plausible. The event must be pharmacologically or phenomenologically definitive, with use of a satisfactory re-challenge procedure if necessary.
  - Probably Related: There is evidence to suggest a causal relationship, and the influence of other factors is unlikely. The clinical event, including an abnormal laboratory test result, occurs within a reasonable time sequence to administration of the study agent/intervention, is unlikely to be attributed to concurrent disease or other drugs or chemicals, and follows a clinically reasonable response on withdrawal (de-challenge). Re-challenge information is not required to fulfill this definition.
  - Possibly Related: There is some evidence to suggest a causal relationship (e.g., the event occurred within a reasonable time after administration of the trial medication). However, the influence of other factors may have contributed to the event (e.g., the subject's clinical condition, other concomitant events). Although an adverse drug event may rate only as "possible" soon after discovery, it can be flagged as requiring more information and later be upgraded to probable or certain as appropriate.
  - Unlikely: A clinical event, including an abnormal laboratory test result, whose temporal relationship to study agent/intervention administration makes a causal relationship improbable (e.g., the event did not occur within a reasonable time after administration of the trial medication) and in which other drugs or chemicals or underlying disease provides plausible explanations (e.g., the subject's clinical condition, other concomitant treatments).
  - Not related: The AE is completely independent of study agent/intervention administration, and/or evidence exists that the event is definitely related to another etiology. There must be an alternative, definitive etiology documented by the clinician.

- **Response to possibly, probably, or definitely related AEs and SAEs:** SAEs determined to be probably or definitely related will prompt discontinuation of study drug. AEs determined to be probably or definitely related with prompt a) decrease in study drug from twice a day to once a day if currently dosing twice daily, b) discontinuation of study drug if only taking once daily, or c) discontinuation for study drug at the discretion of the investigator.
- **Anticipated Adverse Events:** Adverse events are not expected from any of the study procedures. We do not expect any serious adverse events due to losartan.
- **Recording and Documentation**
  - At each contact with the subject, personnel must seek information as to discomforts or adverse experiences by specific questioning and, as appropriate, by examination. This will typically occur via phone or telemedicine due to concerns regarding infectious contagion. Information about AEs to be recorded includes event description, time of onset, investigator assessment of severity, relationship to Study Agent(s)/Intervention(s), and time of resolution/stabilization of the event. All AEs occurring during the study period (from time of consent signing to study day 15) must be documented appropriately regardless of relationship to study products or procedures unless included on the list of clinical outcomes that may be exempt from adverse outcomes reporting as part of the study protocol and outcomes. Information on all identified AEs will be recorded within 5 days of recognition in the appropriate AE module of the case report form (CRF) on Redcap, and within 24 hours in the event of a SAE.

18.3 **Data Safety Monitoring:** A data safety monitoring board (DSMB) has been convened and includes 4 individuals meeting the key element criteria below, and includes a biostatistician with prior clinical trials DSMB experience. The DSMB will follow the guidance as outlined in the application and the attached charter unless there is a compelling, unanticipated reason to deviate from these rules. Data regarding the primary outcome (hospitalization) will be reported to the DSMB continuously, consistent with continuous study monitoring principles. The DSMB may recommend stopping the trial early only for safety, following these guidelines:

[Patient Safety] A recommendation to suspend, alter the study, or stop for harm would occur if during continuous monitoring there is strong evidence that the rate of IRB-reported SAEs was significantly higher in the experimental group than in the placebo group. SAEs (including increasingly level of ventilator support and initiation of vasopressors, the two SAEs of interest) will be reported within 24 hours, allowing for continuous study monitoring. For the inpatient cohort, we propose formal interim analyses for safety at 10%, 20%, and 30% of enrollment. A 50% preplanned interim analysis for safety, efficacy, and futility is planned with specific stopping rules provided to the DSMB as a guide. Assuming a baseline mortality rate of 10%, this corresponds to formal hypothesis testing after every ~2 events initially, and decreasing as data accumulate. Despite the lower number of formal preplanned analyses, the DSMB will still receive near *real-time reporting of deaths*, and can deviate from this strategy and perform earlier testing if desired.

They retain authority to change this plan if the continuous reporting suggests harm prior to the first formal planned assessment if they feel that a formal hypothesis test is warranted. In addition, the DSMB may request additional safety assessments after the 50% assessment, if they feel that additional formal testing is needed.

[Efficacy] – A preplanned interim analysis at 50% of enrollments will assess for early efficacy or futility.

The DSMB will operate in accordance with guidelines established by the FDA in “Guidance for Clinical Trial Sponsors: Establishment and Operation of Clinical Trial Data Monitoring Committee” jointly published by the CBER, CDER and CDRH of the FDA (<https://www.fda.gov/regulatory-information/search-fda-guidance-documents/establishment-and-operation-clinical-trial-data-monitoring-committees>) . The key elements include:

1. Expertise and independence: The members must have expertise in the area of study, not be study authors and have no financial conflict of interest.
2. Members will sign a confidentiality agreement.
3. It is preferred that the DSMB have a face-to-face initial meeting, but can meet by telephone thereafter more frequently.
4. All meetings must follow standard operating procedures (SOPs).

If the DSMB recommends closure of the study, then the DSMB Chair will email the principal investigator and IRB. If the trial is stopped for patient safety and a repairable cause of unacceptably high adverse events can be identified, the action must be reviewed and approved by the DSMB and IRB prior to resuming enrollment. For example, if one additional exclusion criterion is discovered that would account for the majority of unexpected events, this new exclusion criterion could be added, and the study could proceed.

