  - Comorbidities [hypertension (requiring or not requiring medication), diabetes mellitus (insulin or non-insulin dependent), coronary artery disease, myocardial infarction, congestive heart failure (with preserved or reduced ejection fraction, if known), pacemaker or AICD, asthma (with or without emergency department evaluation and / or hospital admission in the past year), chronic obstructive pulmonary disease, chronic bronchitis, chronic steroid use, history of transplant (with type), arrhythmias including atrial fibrillation, dialysis, angina, pulmonary hypertension and obstructive sleep apnea, renal disease, liver disease, tobacco and alcohol use history, recent pregnancy or breastfeeding history, height and weight]
  - Home medications [antihypertensives, insulin, non-insulin diabetes medications, corticosteroids (inhaled or systemic), other immunosuppressants, Use of outpatient COVID-directed

MEDICAL PROTOCOL (HRP-590)

SHORT PROTOCOL TITLE: Randomized control trial of losartan for inpatients with COVID-19

VERSION DATE:22APR2020

- treatments (such as hydroxychloroquine, Tylenol, ibuprofen, azithromycin, or others) or home oxygen use
- Concurrent inpatient medications, including COVID-directed treatments, as well as study medication administration timing
- PROMIS Pool v1.0 Dyspnea Characteristics Survey (5 question Likert scale survey) (attached) with date/time of administration
- Short form 12 health survey (attached) with date/time of administration
- Nasopharyngeal or oropharyngeal swab every third day (performed, yes or no, reason if not)
- Research blood samples (performed, yes or no, reason if not)
- Hospital and ICU utilization (with discharge date, if applicable)
- Clinical laboratory results daily for 10 days, if available (creatinine, total bilirubin, platelet count, white blood count, hemoglobin, sodium, potassium, chloride, glucose, lactate, procalcitonin, albumin, AST, ALT, partial pressure of oxygen on arterial blood gas, troponin, BNP or proBNP, urine pregnancy test, influenza or viral testing results)
- Radiographic findings of CXR, CT chest
- EKG QTc (if performed)
- Ventilatory support: type of ventilatory support (nasal cannula, high flow nasal cannula, face mask, CPAP, BiPAP, endotracheal intubation, ECMO), fraction of inspired oxygen, oxygen flow rate (if applicable), ventilator settings (if applicable, including tidal volume and PEEP)
- Vasopressor usage (daily type and dose)
- Need for renal replacement therapy

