**3.2 Secondary Endpoint(s)/Event(s)/Outcome(s):**

**3.3** There will be 7 secondary endpoints:

- To ensure losartan is safe and well tolerated in hospitalized patients with COVID-19, we will:
  - Compare daily hypotensive episodes (MAP < 65 mmHg) prompting intervention (indicated by a fluid bolus  $\geq 500$  mL)
  - Hypotensive episodes requiring intervention (vasopressors or fluid bolus)
  - Determine the incidence of new or worsening renal failure

- Daily Sequential Organ Failure Assessment (SOFA) score to day 10. If data are unavailable for any given organ failure, we will use the last value carried forward approach.
- Change in estimated P/F ratio daily between groups
- In-hospital, 28, and 90-day mortality (by using state death certificate or social security death index data)
- Resource utilization as assessed by: ICU admission, ventilator free days, oxygen free days, vasopressor free days, ICU and hospital length of stay
- Respiratory failure as measured by the utilization of Bilevel Positive Airway Pressure (BiPAP), high flow nasal cannula, mechanical ventilation or extracorporeal membranous oxygenation (ECMO) utilization, as well as trends in S/F ratio.
- Symptomatic improvement as assessed by the dyspnea PROMIS and SF-12 assessments of dyspnea and functional status
- Percentage of subjects reporting each severity rating on the *7-point ordinal scale* [ Time Frame: Day 15 ]
  - The *7-point ordinal scale* is an assessment of the clinical status at the first assessment of a given study day. The scale is as follows: 1) Death; 2) Hospitalized, on invasive mechanical ventilation or extracorporeal membrane oxygenation (ECMO); 3) Hospitalized, on non-invasive ventilation or high flow oxygen devices; 4) Hospitalized, requiring supplemental oxygen; 5) Hospitalized, not requiring supplemental oxygen; 6) Not hospitalized, limitation on activities; 7) Not hospitalized, no limitations on activities.
  - Change in viral load (nasopharyngeal or oropharyngeal swab and blood)

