molecular docking analysis of the coronavirus macrodomain. We propose a dose increase to 100 mg daily (50 mg PO BID in patients without renal dysfunction). We have previously utilized this dose in previous RCTs in HIV ([name]/[name]). These studies confirmed the safety profile of Losartan with a mean systolic blood pressure (SBP) reduction of only 7 mmHg at 100 mg daily and excellent tolerability and safety profile. Our findings confirm prior reports of 6 mmHg mean SBP reduction for Losartan when doses at 100mg daily. Patients will receive intensive safety monitoring as this will be delivered in the inpatient setting with blood pressure checks multiple times per day and minimum required potassium, creatinine and GFR checks prior to enrollment, day 1, 3, and 7 (or prior to discharge). In addition, patients will have routine creatinine and potassium monitored if ordered clinically. We hypothesize significant benefit as 4 preliminary and observational reports out of China and the UK suggest significant reductions in disease severity and inflammatory profile for patients treated with ACEi or ARBS with no preliminary reports suggesting harm from ACEi or ARBS in Covid19 patients.

- We propose a dose of 50 mg twice daily, given significantly improved RAS blockade. This is a higher dose than we are proposing for study in outpatients, as patients will be carefully monitored with regular blood pressures and renal function testing. Furthermore, patients will have a higher severity of illness and are more likely to benefit from more robust blockade. Patients with moderate renal dysfunction (eGFR 30-59 mL/min/1.73 m^2) will be given 50 mg once daily given impaired renal clearance.

4.2 *Placebo arm:* The same volume of suspension prepared according to the package insert will be administered without the active ingredient. Any unused doses of placebo will be discarded if unused by the 28 day time point.

4.3 *Investigational new drug:* The study will be conducted under IND 148365.

4.4 *Timing of the intervention:* Treatment will continue for 10 days or hospital discharge.

4.5 *Duration of study participation:* The final follow-up will occur at 90 days after randomization to determine episodes of delayed hospitalization. Data analysis is expected to be completed within 1 year of enrollment of the final patient.

4.6 *Drug Handling, blinding, and randomization:*

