## MEDICAL PROTOCOL (HRP-590)

SHORT PROTOCOL TITLE: Randomized control trial of losartan for inpatients with COVID-19

VERSION DATE:22APR2020

\*\*In women of child-bearing age, patients must confirm negative test with study personnel prior to beginning treatment as well as confirmation of acceptable birth control method

\*\*\* A subset of patients will opt-in to an additional pharmacokinetic substudy

\$ Record clinical potassium and creatinine. Required measurements occur pre-enrollment, day 1, day 3 (+/- 1 day), day 7 (+/- 1 day).

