### 8.3 *Exclusion Criteria*

- Randomization  $> 48$  hours of admission order or positive test result, whichever is later
- Currently taking an angiotensin converting enzyme inhibitor (ACEi) or Angiotensin receptor blocker (ARB)
- Prior reaction or intolerance to an ARB or ACE inhibitor, including but not limited to angioedema
- Pregnant or breastfeeding women
- Lack of negative urine or serum pregnancy test
- Not currently taking a protocol allowed version of contraception: intrauterine device, Depo-formulation of hormonal contraception (e.g. medroxyprogesterone acetate / Depo-Provera), subcutaneous contraceptive (e.g. Nexplanon), daily oral contraceptives with verbalized commitment to taking daily throughout the study period; use of condoms or agree to abstain from sexual intercourse during the study. All women of child bearing age enrolled in this fashion will be informed of the teratogenic risks. If enrolled under LAR, they will be informed of the risks after regaining capacity.
- Patient reported history or electronic medical record history of kidney disease, defined as:
  - Any history of dialysis
  - History of chronic kidney disease stage IV

- Estimated Glomerular Filtration Rate (eGFR) of < 30ml/min/1.73 m^2 at the time of randomization
- Severe dehydration at the time of enrollment in the opinion of the investigator or bedside clinician
- Most recent mean arterial blood pressure prior to enrollment <65 mmHg
- Patient reported history or electronic medical record history of severe liver disease, defined as:
  - Cirrhosis
  - History of hepatitis B or C
  - Documented AST or ALT > 3 times the upper limit of normal measured within 24 hours prior to randomization
- Potassium >5.0 within 24 hours prior to randomization *unless* a repeat value was <=5.0
- Treatment with aliskiren
- Inability to obtain informed consent from participant or legally authorized representative
- Enrollment in another blinded randomized clinical trial for COVID

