## **13.0 Risks to Participants**

*13.1 Foreseeable Risks:* Potential risks of losartan are detailed in consent forms. The most severe risks of losartan use include teratogenicity in the setting of pregnancy, hypersensitivity including angioedema, symptomatic hypotension, worsening of renal function, and electrolyte abnormalities. The most common side effects of losartan include fatigue, weakness, diarrhea, chest pain and anemia. Subjects will be rigorously screened to ensure that they are at low risk for complications due to losartan and they will be monitored closely for side effects and signs of toxicity. The package insert for Losartan has been included with this protocol. Clinical trial and post-marketing surveillance data (see package insert) demonstrate an

excellent safety profile. In over 4,000 patients, there was a low incidence of adverse events (2.3%) comparable to placebo (3.7%). The effects more common in losartan than placebo were clinically minor, including dizziness (3% vs 2%), upper respiratory infection (8% vs 7%), nasal congestion (2% vs 1%) and back pain (2% vs 1%). While losartan has the potential to cause symptomatic hypotension, four studies have identified losartan has a negligible effect on resting blood pressure and heart rate in healthy volunteers. While there may be a higher risk in critically ill patients, we will exclude patients with bedside clinician assessment of volume depletion that might increase the risk of side effects. It has been theorized there may be an increase risk of cardiac dysfunction in patients taking an ACE-I or ARB in COVID-19, though evidence for this effect is lacking. We will monitor troponin and BNP/pro-BNP levels in participants and report these data to the DSMB if measured clinically. In fact, the most recent preprinted (non-peer reviewed) data from China now suggest a protective effect based on retrospective data compared to other antihypertensive regimens. Nevertheless, based on this recent suggestion, we will track troponin and BNP/proBNP measurements in addition to our previously planned assessments of new episodes of hypotension and shock, and report these data to the DSMB. In addition, all patients are closely monitored for clinical purposes given their severity of illness, combined with daily assessments for AEs and SAEs will allow for early detection of side effects and reduce the risks to patients.

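### Potassium changes are exempt from adverse event recording as tracked outcomes, but no outcome or analysis uses potassium, so a non-serious treated rise judged unrelated can go unreported

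*Combined protocol and SAP*

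**What the plan says.** **Risk.** Section 13.1 includes "symptomatic hypotension, worsening of renal function, and electrolyte abnormalities" among the most severe risks of losartan. Section 8.3 excludes "Potassium >5.0 within 24 hours prior to randomization" unless a repeat is 5.0 or lower.

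**Measurement.** Section 4.1 and the footnote to the table in 5.6 require potassium before enrollment and on days 1, 3 and 7. The footnote allows one day either side for days 3 and 7, and 4.1 allows a pre-discharge value instead. The table limits these procedures to inpatients. Section 1.6 also collects "Clinical laboratory results daily for 10 days, if available", and potassium is on that list.

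**AE reporting.** Section 18.2 exempts a list of events that includes "Changes in serum sodium and potassium". The exemption lapses if the event is judged related or of uncertain relationship, or leads to discontinuation of study procedures. The reason given is: "The following are examples of events that will be considered study specific clinical outcomes and will be systematically tracked through the study design". The outcomes are said to be those in 5.1 and 5.2. The recording paragraph of 18.2 repeats the exemption.

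**Outcomes and analysis.** The safety items in 3.3 are two hypotension measures and "Determine the incidence of new or worsening renal failure". Section 15.1 covers the primary and secondary endpoints and describes no laboratory or AE analysis.

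**The concern.** The exemption is a trade: a listed event leaves the AE log because a systematic outcome will catch it. For potassium the first half is written down and the second is not. Whether a rise is reported then depends partly on attribution.

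The protocol itself distrusts that route. The exemption paragraph calls relatedness subjective and AE reporting inconsistent. Section 3.4 tracks hypotension and kidney injury systematically because relying on AE reports can introduce bias. The same reasoning applies to potassium, which has its own entry limit and required draws. At stake is whether the trial reports an attribution-free comparison for one of the risk classes it names.

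**Working it through.** **1. Does the cross-reference lead to a potassium outcome?** No. Sections 5.1 and 5.2 are Screening and Enrollment. The outcomes are in section 3, and none of 3.1-3.3 mentions potassium.

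**2. Does any analysis use it?** No. Section 15.1 analyses endpoints only.

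**3. Does the data safety monitoring board (DSMB) route fill the gap?** Not by name. Continuous reporting in 18.2 covers deaths, cardiovascular events and respiratory events, and 13.1 adds troponin and BNP. The harm guideline in 18.3 turns on SAEs.

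**4. What happens to each kind of potassium event under 18.2?**

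- *Judged related or of uncertain relationship:* reported, because the exemption lapses.
- *Leads to discontinuation of study procedures:* reported, for the same reason.
- *Serious:* SAEs are collected to day 15 regardless of causation. How this interacts with the exemption is not stated.
- *Non-serious, treated, judged unrelated, study procedures continued:* the rules conflict. The AE definition counts an abnormal result that leads to additional treatment, and the laboratory paragraph counts one needing active management. The exempt list and the recording paragraph take it out.

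Only the last group can be absent from both the AE table and every planned comparison.

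**5. What could a comparison show?** The documents give no potassium figure to reproduce and state no alpha. I use two-sided 0.05 and n = 100 per arm (minimum 200 in 10.2, 1:1 allocation in 4.6). These inputs reproduce the plan's only power claim (15.2: above 0.8 for a P/F difference of 50 with SD 125). The standard error is 125 × √(2/100) = 17.68, 50/17.68 = 2.828, and Φ(2.828 − 1.960) = 0.807.

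For two proportions with mean p̄:

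Power = Φ{ [(p₂ − p₁) − 1.96·√(2p̄(1 − p̄)/n)] / √([p₁(1 − p₁) + p₂(1 − p₂)]/n) }

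The 95% half-width is 1.96 times the denominator. The event rates are assumptions.

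| Placebo v losartan | Null SE | Alternative SE | Power | 95% half-width (points) |
|---|---|---|---|---|
| 5% v 10% | 0.0372 | 0.0371 | 0.27 | 7.3 |
| 5% v 15% | 0.0424 | 0.0418 | 0.66 | 8.2 |
| 5% v 20% | 0.0468 | 0.0456 | 0.90 | 8.9 |

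Other assumed rates give power of 0.30 (2% v 6%), 0.51 (10% v 20%) and 0.80 (10% v 25%).

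If only half the events in each arm reached the AE log, which is also an assumption, 5% v 15% would appear as 2.5% v 7.5% (power 0.37). Likewise 5% v 20% would appear as 2.5% v 10% (power 0.59).

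**The case against.** **The exemption is not a blanket one.** This stands. Events of uncertain relationship are still reported. The attribution scale in 18.2 requires a documented, definitive alternative cause for the category of not related, and SAEs are collected whatever their cause. A reader might infer that only events a blinded investigator blames on the drug survive. The text does not support that.

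**The AE definition and laboratory paragraphs already catch treated rises.** This stands in part. A reader might infer that the exempt list overrides them. The recording paragraph points that way, but nothing states which rule prevails, so sites could follow either.

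**Hyperkalaemia is not named as a severe risk.** Correct. Section 13.1 names electrolyte abnormalities as a class. The link to high potassium is an inference from the 5.0 exclusion.

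**Potassium is tracked, and the values can be tabulated later.** The values are indeed collected, and nothing forbids tabulating them. What is missing is a prespecified outcome. A threshold and time point chosen after unblinding would be post hoc.

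**Sodium sits in the same bullet with the same gap.** True, but sodium has no exclusion limit and no required draws of its own.

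**The highest value, or any value above 5.0, would be the obvious comparison.** It is a poor main choice. Draws are inpatient only, so patients who stay longer have more chances to cross the limit, and length of stay is itself an outcome in 3.3.

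**Conclusion.** The concern holds in limited form. Section 18.2 exempts potassium changes from AE recording on a ground the plan does not meet: the cited sections define no outcome, and no endpoint or analysis uses potassium. Other paragraphs of 18.2 conflict with the exemption. The events exposed are non-serious treated rises judged unrelated.

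The documents do not show that all potassium events would be lost, that serious ones would be, or that a difference between arms exists. The size of the loss cannot be calculated from them, because it depends on unstated event rates and on attribution. The power figures rest on assumed rates, two-sided 0.05 and all 100 per arm evaluable. Early discharge would reduce the evaluable number. A doubling from 5% would usually be missed (power 0.27), so the value lies in an estimate free of attribution. The plan should be changed on this point, since the data needed are already collected.

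**What to change.** 1. In 18.2, reconcile the AE definition and laboratory paragraphs with the exempt list and the recording paragraph for potassium. Correct the reference to 5.1 and 5.2.
2. Add to 3.3 and 15.1 a by-arm potassium safety summary, regardless of attribution:
   - *Main:* the difference between arms, with 95% CI, in potassium at the required day 3 draw, or the last value before discharge if earlier, adjusted for the pre-enrollment value.
   - *With it:* the proportion above the protocol's own 5.0 entry limit at that draw, used only as an analysis cut-off.
   - *Supportive:* the day 7 and any-value versions, with the number of draws per arm, because these depend on length of stay.
   - *Missing data:* the number in each arm without a usable value.
3. If no potassium outcome is added, remove potassium from the exempt list.

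Day 3 suits the main comparison because the protocol's rationale for endpoint timing puts steady state beyond 24 hours and average stay at 10 days. Most patients should therefore still be in hospital.

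The cost is a few lines of text, one table and one more secondary comparison of limited power. No new draws are needed. No dose or treatment rule is proposed.
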